3.4 Sample Size

The sample size for the quasi-experimental pre-post study is calculated separately for each country, based on comparison between pre- and post-intervention periods. The following assumptions are used:

- ξ power 80%
- ξ alpha level of 0.05
- ξ pre-intervention referral to a higher level of care 3%, with a minimum detectable difference of 50%
- ξ pre-intervention antibiotic prescription of 60%
- ξ intra-cluster correlation coefficient (ICC) of 0.005 for referral and 0.05 for antimicrobial prescription
- ξ Kenya – estimated average cluster size of 230 children / month (assuming a cluster ratio of health centres : dispensaries 1:2, with 100 / month in dispensaries and 500 / month in health centres)
- ξ Senegal – estimated cluster size of 170 children per month

For the referral primary outcome, we therefore initially estimated requiring the following sample size:

- ξ Kenya – 17 facilities, recruiting an average of 690 children per quarter per facility, equating to 11,730 children per quarter
- ξ Senegal – 18 facilities, recruiting an average of 510 children per quarter per facility, equating to 9,180 children per quarter

For the antibiotic prescription primary outcome, this would enable a minimum detectable reduction of 18% in Kenya and Senegal.

Following lower than anticipated recruitment in the pre-intervention period, sample size calculation was revised. As a result, two additional facilities were added per country and the pre-intervention period was extended from an initially anticipated 3 months to a 6 – 8 month period. A decision was also taken to target a post-intervention sample size of at least the same as the pre-intervention sample size, as well as a minimum duration of 9 months post-intervention to allow for stabilisation over time and some seasonal overlap of pre- and post-intervention periods.

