3.7 Timing for Analysis

The final analysis will take place once all children have received a minimum of 7 days of follow-up. A pooled cross-country analysis will be conducted as well as individual country analyses.

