4 STATISTICAL PRINCIPLES

4.1 Confidence Intervals and p-Values

Results estimates of primary and secondary outcomes will be presented along with the associated two-sided 95% confidence intervals.

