6 ANALYSIS

Analyses will be performed and reported overall and by country.

Outcomes will be presented separately for young infants (<60 days) and older children (60 days-59 months), the malaria-related outcomes will be presented only on older children.

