6.1.1 General definitions

Day 7 assessment

Day 7 assessment refers to information reported by the caregiver after Day 0 and recorded in Day 7 form. Data collected as part of unscheduled visits are also integrated in these forms. If multiple successful follow-up assessments for the same child are recorded within the Day7 database, the most recent follow-up assessment will be used. To limit potential recall bias, assessments conducted far beyond the expected follow-up time will be dropped, i.e. 30 days from Day 0.

Death

A child will be considered deceased if, from Day 7 assessment, his/her status at the time of follow-up is “deceased”. In case of implausible death date (i.e. prior to enrolment date), death will be assumed to be within 7 days of Day0.

Hospitalisation

A child will be considered hospitalised if, from Day 7 assessment, he/she went to a hospital, was admitted overnight or if his/her status at the time of follow-up is “hospitalised”. In case of implausible hospitalisation date (i.e. prior to enrolment date), hospitalisation will be assumed to be within 7 days but after 24hrs of Day0.

Hospitalisation within 24hrs of Day0

For the purpose of primary analysis, a child will be considered admitted to hospital within 24hrs of Day0 consultation if the date of hospitalisation is the same as Day0 date or is one day after Day0 date.

Referral

A child will be considered to be referred (either to a hospital or to an inpatient part of a larger primary healthcare facility) if, at Day0, the research assistant confirms that an urgent referral advice was recorded for the child. If urgency is unknown, referral will be assumed to be urgent.

Antibiotics

Antibiotics will be defined in accordance with the WHO antibiotic point prevalence survey (PPS) methodology [4, 5, 6] and therefore only antibacterials for systemic use will be taken into account.

SpO2 values

SpO₂ should be recorded during the Day0. For the outcomes, the following measures will be taken for spurious and missing SpO₂ values:

- If SpO₂ value is not available, the child will be assumed normoxaemic
- If $70 \leq \text{SpO}_2 < 90\%$, the child will be assumed (with accuracy) to have severe hypoxaemia
- If $40 \leq \text{SpO}_2 < 70\%$, the child will be assumed (with low accuracy) to have severe hypoxaemia
- If $\text{SpO}_2 < 40\%$, the value will be considered spurious (e.g. due to incorrect dataentry) and treated as not available, i.e. the child will be assumed normoxaemic.

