6.1.2.3 Average length of stay (in days) of children admitted to hospital

Length of stay is defined as hospitalisation duration in days as reported by the caregiver at Day 7. If a child is hospitalised twice, the first hospitalisation will be used and second hospitalisations will be reported separately. The denominator will be all hospitalised children.

6.1.2.4 Proportion of children referred by a primary healthcare provider to a higher level of care at Day 0 consultation

All children who received a referral advice (as per definition above) at Day0 will be counted in the numerator. The denominator will be all children recruited.

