6.2.4 Pre-planned Sensitivity Analyses

Sensitivity analyses on the primary outcomes are planned and will be conducted:

- ξ On first encounters, which will include only the first enrolment episode of each child during the study period (as some children may attend the facility on more than one occasion). Separate presentations are identifiable from Day0 form as the caregiver is asked whether the child attended previously and within 28 days. This is the minimum number of days required for the disease episode to be considered a new one and not a repeat visit.
- ξ Looking at different referral definitions¹:
 - ο A child will be considered to be referred if, at Day0, the caregiver confirms that the child was urgently referred or the research assistant confirms that an urgent referral advice was recorded for the child. If urgency is unknown from both sources, referral will be assumed to be urgent.

¹ Urgency, as reported by the caregiver, was introduced only in the post-intervention period in Kenya. For the pre-intervention period, urgent referrals will be defined based on the registry alone, as described for the primary analysis.

- A child will be considered to be referred if, at Day0, caregiver confirms that the child was urgently referred *and* the research assistant confirms that an urgent referral advice was recorded for the child.

Additionally, a set of sensitivity analyses shall be carried out based on different definitions of pre and post-intervention periods:

- ξ Pre-intervention and post-intervention defined based on periods of the year that match in the pre and post intervention.
- ξ Pre-intervention defined as primary analysis and post-intervention from country-specific relevant dates (i.e. formal initiation after the strike in Senegal and intensive supervision in Kenya) to the end of data collection.

Sensitivity analyses on the secondary outcomes related to hospitalisation will be conducted looking at different hospitalisation appropriateness (based on different definitions of primary and secondary hospitalisations). Same day (Day0), 3 days and 7 days from Day0 will be used as cut-offs for different primary and secondary hospitalisation definitions.

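### In Kenya, both alternative referral definitions change only the post-intervention count, so they do not test the definition there, and this carries partly into the pooled result

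*SAP*

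**What the plan says.** The primary referral definition (SAP 6.1.1) rests on the registry: the research assistant confirms that urgent referral advice was recorded. Where the registry does not show urgency, the rule is "If urgency is unknown, referral will be assumed to be urgent". SAP 6.1.2.4 sets the numerator, "All children who received a referral advice (as per definition above) at Day0 will be counted in the numerator", over all recruited children.

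SAP 6.2.4 adds two alternatives:

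- **Either-source rule:** urgent according to the caregiver or the registry. Urgency unknown from both sources counts as urgent.
- **Both-sources rule:** urgent according to the caregiver and the registry. No rule for unknown urgency is given.

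Footnote 1 is attached to the bullet that introduces both rules. It says "Urgency, as reported by the caregiver, was introduced only in the post-intervention period in Kenya", and then: "For the pre-intervention period, urgent referrals will be defined based on the registry alone, as described for the primary analysis". The second sentence names no country.

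On reporting, SAP 6 says "Analyses will be performed and reported overall and by country", and SAP 3.7 says "A pooled cross-country analysis will be conducted as well as individual country analyses". The SAP gives no guidance on reading the Kenyan results of these two analyses and does not exclude them from the overall result.

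**The concern.** A sensitivity analysis of an outcome definition in a pre-post study should apply the alternative definition in both periods. Otherwise the contrast mixes the intervention effect with a change in measurement. In Kenya the pre-intervention numerator is the same in the primary analysis and in both alternatives, so any crude movement away from the primary estimate is post-period reclassification.

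The other planned sensitivity analyses of the primary outcomes vary the encounters included or the period dates. These two are the only ones that vary how referral is defined. If they are reported without a caution, a shrunken both-sources estimate could be taken as fragility of the referral effect, and an enlarged either-source estimate as support for it. Reclassification alone could produce either.

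**Working it through.** **Inputs from the documents.** SAP 3.4 gives "pre-intervention referral to a higher level of care 3%, with a minimum detectable difference of 50" per cent, so p0 = 0.03 and the planned p1 = 0.03 × 1.5 = 0.045. Protocol 6.6.1 gives initial sizes per period of 11,730 (Kenya) and 9,180 (Senegal), an ICC of 0.005 for referral, alpha 0.05 and power 80%.

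**Inputs not in the documents.** The caregiver/registry discordance d is assumed at 10%, 20% and 30% of registry-defined referrals. It is a net gain under the either-source rule and a loss under the both-sources rule; the two need not be equal in practice. The share k of registry referrals with unknown urgency is assumed at 5%, 10% and 20%.

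**Step 1: reproduce the plan's figure.** The two-proportion formula (two-sided, no continuity correction) gives 2,518 children per period before clustering.

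- Kenya: 1 + 689 × 0.005 = 4.445; 2,518 × 4.445 = 11,193; 11,193 / 690 = 16.2, so 17 facilities and 17 × 690 = 11,730.
- Senegal: 1 + 509 × 0.005 = 3.545; 2,518 × 3.545 = 8,926; 8,926 / 510 = 17.5, so 18 facilities and 18 × 510 = 9,180.

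Both match. This fixes only the base rate and the country weights: Kenya 11,730 / 20,910 = 56%, Senegal 44%.

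**Step 2: direction.** Every both-sources case is also a primary case, so Kenya's crude post-intervention rate can only fall or stay the same. The registry-only pre rate is at least as high as a both-sources pre rate would have been. The crude Kenyan both-sources odds ratio is therefore a lower bound for the like-for-like one. The either-source rule usually raises the post rate, but not necessarily: a referral of unknown registry urgency that the caregiver calls non-urgent counts in the primary analysis but not under this rule as worded.

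**Step 3: crude size.** Odds ratio = [p1/(1 − p1)] / [p0/(1 − p0)]. For example, with no true effect, d = 20% and the either-source rule in Kenya: (0.036/0.964) / (0.030/0.970) = 1.21. For the pooled value, Senegal is shifted in both periods, so the pre rate is 0.561 × 0.030 + 0.439 × 0.036 = 0.0326, and (0.036/0.964) / (0.0326/0.9674) = 1.11.

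| Scenario | Rule | d = 10% | 20% | 30% |
|---|---|---|---|---|
| Kenya, no true effect (like for like 1.00) | either | 1.10 | 1.21 | 1.31 |
| | both | 0.90 | 0.80 | 0.69 |
| Pooled, no true effect (like for like 1.00) | either | 1.06 | 1.11 | 1.15 |
| | both | 0.94 | 0.87 | 0.80 |
| Kenya, 3% to 4.5%, as planned in the SAP | either | 1.68 | 1.85 | 2.01 |
| | both | 1.36 | 1.21 | 1.05 |
| Kenya, 3% to 4.5%, like for like | either | 1.53 | 1.53 | 1.53 |
| | both | 1.52 | 1.52 | 1.52 |

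At d of one third, the planned Kenyan effect disappears under the both-sources rule: 0.045 × 2/3 = 0.030. The sample size was later revised and the final country shares are not given. For a Kenyan share of 40% to 70% at d = 20%, the pooled null value runs from 1.07 to 1.14 (either) and from 0.91 to 0.85 (both).

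**Step 4: unknown urgency alone.** Suppose the sources agree on every referral of known urgency, but the both-sources rule drops unknowns after the intervention while Kenya's pre period counts them as urgent. With p1 = 0.03(1 − k) against 0.03, the null odds ratio is 0.95, 0.90 or 0.80 for k = 5%, 10% or 20%.

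**The case against.** The strongest reply is that the SAP discloses the limitation: the footnote says which item was missing, where and when, and what replaces it. By-country reporting will show Senegal on its own. That stands as far as it goes, but disclosure gives no direction of bias and does not keep the mixed Kenyan contrast out of the overall result.

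A second reply is that the size is unknown. This stands in full: every discordance figure above is an assumption, and the shift at 10% is small. SAP 4.1 says "Results estimates of primary and secondary outcomes will be presented along with the associated two-sided 95% confidence intervals", so the figures concern point estimates and no error rates are claimed.

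A third is that the unknown-urgency gap is arguable. Read literally, the both-sources rule excludes unknowns; read with the general definitions in 6.1.1, it may count them as urgent. The text is ambiguous, and Step 4 applies only to the first reading.

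A fourth is that the lower bound in Step 2 holds for crude proportions only. The planned model is covariate-adjusted with a random effect, and SAP 6.2.1 allows clusters to be dropped or combined if data are sparse, so the two analyses may not even use the same facilities. This also stands.

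A reader might infer that the pooled estimate, too, is redefined only after the intervention. The documents do not support that on the natural reading: the footnote names only Kenya as lacking the item, which leaves Senegal redefined in both periods and the pooled shift at about half of Kenya's.

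**Conclusion.** The point holds for Kenya and partly for the pooled result. In Kenya, a reduced both-sources effect or an enlarged either-source effect cannot be read as a test of the referral definition. At an assumed 20% discordance and no true effect, the crude odds ratio would be 1.21 or 0.80 in Kenya and 1.11 or 0.87 pooled, instead of 1.00. With perfect agreement and no unknown urgency it would not move.

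Two stronger inferences should be avoided. The Kenyan analyses are not worthless: on crude proportions, an increase that survives the both-sources rule is conservative evidence of an increase under that rule applied in both periods. And the primary referral result is not in doubt on this ground, because it uses the registry in both periods; the antibiotic outcome is not touched.

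The conclusion rests on the footnote's second sentence applying to Kenya alone. If it also covers Senegal, no like-for-like comparison exists in either country. This is a minor point.

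**What to change.** 1. Confirm in the SAP that caregiver-reported urgency was collected in both periods in Senegal, and name the country in the footnote's second sentence.
2. If so, run the either-source and both-sources comparisons like for like in Senegal only, and leave Kenya out of any pooled version.
3. If Kenya is kept, report it separately and label it directional. The both-sources result is a conservative lower bound on crude proportions, which is not guaranteed for the adjusted random-effects odds ratio. The either-source result is not comparable across periods. Add a table of Kenyan post-intervention caregiver/registry agreement (urgent, non-urgent and unknown, by source).
4. State one unknown-urgency rule for the both-sources definition, consistent with SAP 6.1.1, so that unknowns are not counted before the intervention and dropped after it.

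The cost is SAP wording and at most one small table, with no new data and no extra model. The Senegal-only option gives up the conservative Kenyan both-sources check; the labelled option keeps it.

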6.6 Sample size

The estimated sample sizes for each of the studies are described below, but may be revised during the course of the study. In the case of the pre-post study, this is due to uncertainty of some of the assumptions (such as eligibility rate and outcome proportions in routine care, for which data reliability is a challenge). Final qualitative sample sizes will be determined based on reaching thematic saturation, i.e. when no new concepts are emerging.

The remaining sample sizes, for SPA, process mapping and time-flow study, have been chosen pragmatically and will vary according to country depending on the degree of difference in care processes between facility types and location, whilst allowing for exploratory analysis into more in-depth aspects of quality of care from baseline to intervention and over time within the intervention period (both due to changes in implementation uptake and seasonal variation in burden of disease).

The sample size for the pilot phase will also be pragmatically based on the degree of difference between facility types and location (and thus the potential need to understand and refine the intervention strategy according to context), but is likely to include between 2 and 6 facilities per country.

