We will conduct the primary analysis on all visits (for visits by the same child, this implies visits greater than 28 days apart as per the exclusion criteria). However, we will conduct a sensitivity analysis excluding repeat visits of an individual child within the same quarter, to address the possibility that outcomes of children attending for more than one disease episode are correlated and impact the interpretation of the study. Due to the challenge in correctly identifying all repeated visits, the fairly low likelihood of repeat visits (based on available literature) and the acuity of the majority of sick child visits, we do not expect these analyses to produce very different results. We will conduct sensitivity analyses for measured and unmeasured confounders over time to assess robustness of the findings, which will be detailed in the SAP.

An exploratory interrupted time series analysis will be conducted to assess change over time.

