6.2 Analysis Methods

6.2.1 Analytical Methods

For the primary analysis, pre-intervention and post-intervention periods will be defined as follow:

Pre-intervention period: from the date of data collection start to the date healthcare providers left the facilities for training on the intervention

Post-intervention period: from the date healthcare providers returned to the facilities after training and the devices was delivered to the facilities to the end of data collection

As training was staggered for the facilities, the definitions above will be applied at the facility level.

Outcomes will be described for each time period using summary statistics. In particular, counts and percentages will be used for binary variables and reported with one decimal place; mean and standard deviation (SD) or median (IQR) for continuous variables depending on their

distribution. Mean and median will be displayed with one decimal place and SD and IQR will be presented with two decimal places.

The two primary outcomes will be assessed using a random effects logistic regression model with the cluster included as a random effect. If convergence issues arise due to sparse data, clusters may be dropped or combined to higher grouping level (e.g. district).

Results will be reported with odds ratios, risk differences and their associated 95% confidence intervals (CI).

Secondary outcomes and other binary outcomes of interest will be evaluated in the same way.

Other continuous outcomes of interest will be assessed using random effects linear regression model with the cluster included as a random effect. Results will be reported in terms of adjusted mean differences with associated 95% CIs.

Modelling of secondary outcomes will be performed if numbers allow.

Further exploratory analysis, including interrupted time series analysis to assess change over time and data linked between the quasi-experimental pre-post study and the SPA and time-flow studies. These fall outside the scope of this SAP and will be detailed in a separate document.

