6.2.2 Adjustment for Covariates

All models will be adjusted for the following potential confounders: age, sex, travel time to facility, illness duration, clinical presentations, previous care and previous treatment. Further sensitivity analysis may be performed adjusting for additional baseline variables.

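### Does the season check need rewriting, given that the primary pre/post models have no season term and SAP 6.2.4 names neither the matched months nor the matching unit?

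*SAP*

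**What the plan says.** SAP 6.2.1 fits a logistic model of post against pre with facility as a random effect. SAP 6.2.2 adjusts for "age, sex, travel time to facility, illness duration, clinical presentations, previous care and previous treatment". Season, month and calendar time are absent. Period boundaries are local: "As training was staggered for the facilities, the definitions above will be applied at the facility level".

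Protocol 5.2 sets 6–8 months of baseline followed by 9–12 months of intervention. SAP 3.4 explains the 9-month minimum as a way "to allow for stabilisation over time and some seasonal overlap of pre- and post-intervention periods". It also records that "two additional facilities were added per country and the pre-intervention period was extended" after slow recruitment.

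Protocol 7.3.1 promises "sensitivity analyses for measured and unmeasured confounders over time to assess robustness of the findings, which will be detailed in the SAP". On season, the SAP then offers one line: "Pre-intervention and post-intervention defined based on periods of the year that match in the pre and post intervention". A companion analysis moves the follow-up start: "Pre-intervention defined as primary analysis and post-intervention from country-specific relevant dates", these being the formal initiation after a strike in Senegal and intensive supervision in Kenya. The interrupted time series is left to a separate document (SAP 6.2.1).

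**The concern.** There is no concurrent control, so season competes directly with the intervention as an explanation. Adjustment for clinical presentation removes some seasonal case mix, but seasonality within a presentation can remain in the headline odds ratio. The single direct check leaves three things open: which months, whether matching is within facility or by country, and what happens to a facility with no matched month.

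There is also a problem of interpretation. When one period follows the other, the shared months are the first of baseline and the last of follow-up. The protocol itself expects change over time in its sub-studies, "both due to changes in implementation uptake and seasonal variation in burden of disease" (Protocol 6.6). A gap between the primary and matched estimates could be uptake rather than season. Agreement between them could also hide two opposing biases.

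**Working it through.** **1. Reproducing the plan's sample size.** Inputs (Protocol 6.6.1, SAP 3.4): 3% against 4.5% referral, 80% power, alpha 0.05 (taken as two-sided), ICC 0.005. With mean proportion 0.0375, n = [1.96√(2×0.0375×0.9625) + 0.842√(0.03×0.97 + 0.045×0.955)]² / 0.015², which rounds up to 2,518 per period.
- Kenya: design effect 1 + 689×0.005 = 4.445; 2,518×4.445 = 11,192.5; divided by 690 this is 16.2, so 17 facilities and 11,730 children.
- Senegal: design effect 1 + 509×0.005 = 3.545; 2,518×3.545 = 8,926.3; divided by 510 this is 17.5, so 18 facilities and 9,180 children.

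Both match the stated targets.

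**2. Calendar overlap.** With baseline of a months, follow-up of b months and no gap, shared months = a + b − 12, and the first matched follow-up month is 13 − a.

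| a + b | Shared months | Matched follow-up months |
|---|---|---|
| 6+9 | 3 | 7–9 |
| 8+9 | 5 | 5–9 |
| 6+12 | 6 | 7–12 |
| 8+12 | 8 | 5–12 |

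An assumed one-month training gap moves the first matched month one earlier. The matched contrast is therefore early baseline against later follow-up.

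**3. Possible size of a seasonal bias.** The documents give no seasonal amplitude. Assume one annual peak with peak-to-trough odds ratio 1.5 after adjustment, so the logit amplitude is ln(1.5)/2 = 0.2027, with even enrolment. The mean of a 12-month cosine over a window of w months has amplitude (12/πw)·sin(πw/12).
- 6+9: window amplitudes 0.637 and 0.300, centres 7.5 months (225°) apart. The difference is √(0.405 + 0.090 + 2×0.637×0.300×0.707) = 0.875. Worst phase: exp(0.875×0.2027) = 1.19. Averaged over phase (×2/π): 1.12.
- 8+12: the 12-month window averages to zero and the 8-month one has amplitude 0.413. Worst phase: exp(0.413×0.2027) = 1.09. Averaged over phase: 1.05.

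**4. Possible size of an uptake gap.** Design odds ratio (0.045/0.955)/(0.03/0.97) = 1.524. Assume no season and a linear six-month build-up of the log odds ratio.
- 6+9: primary share (3 + 3)/9 = 0.667, odds ratio 1.32; matched share 1.0, odds ratio 1.52; ratio 1.15.
- 8+12: primary share (3 + 6)/12 = 0.75, odds ratio 1.37; matched share (2×0.833 + 6)/8 = 0.958, odds ratio 1.50; ratio 1.09.

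Uptake alone could thus open a gap of the same order as step 3.

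**5. Precision of the matched analysis.** Initial targets spread over 17 + 2 = 19 and 18 + 2 = 20 facilities. The design effect must be recomputed, because matching also reduces the children per facility.
- Kenya 6+9: 11,730×3/6 = 5,865 and 11,730×3/9 = 3,910 children; cluster sizes 308.7 and 205.8; design effects 2.538 and 2.024; effective 2,310 and 1,932; power 73%, against 85% for the full periods.
- Senegal 6+9: 4,590 and 3,060 children; cluster sizes 229.5 and 153; design effects 2.143 and 1.760; effective 2,142 and 1,739; power 69%, against 84%.
- 8+12: 83% and 81%.

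With the initial 17 and 18 facilities, the 6+9 figures are 70% and 67%. Cutting the sample but keeping 4.445 and 3.545 would give about 45–46%, which is too pessimistic.

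**6. What the SAP already settles.**

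| Open point | Where it is met |
|---|---|
| Months | The intersection of pre and post calendar dates, fixed once enrolment dates are known |
| Unit | SAP 6.2.1: periods defined by facility |
| Outcomes and level | SAP 6.2.4, by its placement, covers the primary outcomes; SAP 6 requires results overall and by country |
| How to compare | SAP 4.1: estimates with 95% intervals; no significance rule for sensitivity analyses |
| Uptake | SAP 4.2: adherence weekly by facility; SAP 6.4: primary outcomes by adherence and indication group; SAP 6.2.4: later-start analysis |

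**The case for a change.** The strongest opposing case is that the protocol promised detail in the SAP and the SAP gives one sentence. The SAP is dated 05/04/2023, after the anticipated end of data collection in Q1 2023 (Protocol Summary). If that timeline held, the months could have been listed and discretion closed. The later-start analysis keeps the whole baseline, so it does not match on season, and no joint reading of the two is planned. The two facilities added per country (2 of 19 and 2 of 20) might share few months. If they started three months late, which is an assumption, they share none on a 15-month span and five on a 20-month span.

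The facts stand, and so does the caution that the gap between matched and primary estimates is not season alone. The stronger claim, that the gap cannot be interpreted at all, does not. Weekly facility adherence shows directly whether uptake differed between matched and unmatched months. The build-up and its direction are assumed: Protocol 6.3 puts intensive mentoring straight after training and then tapers it, although the later-start dates in SAP 6.2.4 suggest that full implementation may have come later. The largest figures need the shortest, 15-month span. The same anticipated timeline (first enrolment Q2 2021, completion Q1 2023) covers at least about 18 months, which implies at least six shared months if enrolment was continuous.

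A season term in the primary model would gain little. With month indicators, a month seen in only one period says almost nothing about the period effect, so the estimate would rest mainly on the shared months. That is close to the matched analysis already planned.

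**Conclusion.** No change follows. Using every visit in the primary analysis and checking season on matched months is a fair trade-off in a design with partial calendar overlap. What is left unwritten is a list of months that the dates determine, a unit that SAP 6.2.1 already implies, and a caution that a careful analyst would add when reporting. No stated rule produces a wrong result.

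Under the assumed seasonal odds ratio of 1.5, the spurious primary odds ratio runs from 1.09 (8+12) to 1.19 (6+9) at the worst phase and from 1.05 to 1.12 on average. An assumed six-month build-up of uptake gives a gap of 1.09 to 1.15. Matched-analysis power for referral is about 69–73% (6+9) to 81–83% (8+12). These figures rest on consecutive periods, even enrolment, the initial sample targets and the planning ICC. The planning formula treats the two periods as independent, and recruitment ran below expectation, so true precision could differ either way. Secular trends other than season remain a limit of the design whatever this sentence says.
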